**7.9 \* PROCEDURES / METHODS: (REQUIRED)**

Describe the research methods and study activities taking place at each site (e.g. what will participants be asked to do and what will members of the study team do?). If there will be multiple participant groups or study sites, explain what will happen with each group or study sites.

If some of the activities would occur even if the person were not in the study, as in the case of treatment or tests performed for diagnostic purposes, **clearly differentiate between those activities that will be**

## **done solely for research purposes and those that are happening as part of routine care.**

Please call our office at [contact] and ask to speak to someone on the Expedited Review team if you need help differentiating between what parts are research and what parts aren't.

At UCSF:

As we described in the application for Phase 1 of this study, **MBSR** is a standardized and manualized 8-week program, delivered once a week in 2½-hour group sessions and a daylong retreat. It trains individuals in several mindfulness practices, e.g. focus on breath, varying degrees and directions of object orientation, open monitoring of awareness of intero- and exteroceptive stimuli and thoughts, de-reification (i.e. the notion that thoughts and perceptions are not always true to reality), and meta-awareness (i.e., awareness of thinking) in addition to focused attention. The program typically includes an audio-recording and a book for home practice and has shown benefits in patients with cLBP.

**MBPR** will be an optimized mindfulness program specifically designed for treating cLBP that we aim to develop and test in this project. The format is the same as MBSR: 8 weeks of weekly 2½-hour group sessions and a daylong retreat in smaller groups: 10 participants per class to allow for more individualized support. All sessions include training to enhance mindful interoceptive awareness through focused attention in the region of pain, the lower back. Key goals are to reduce avoidance, rumination, catastrophizing, and fear of movement, all key mechanisms of action in MBSR or CBT. The new elements of these classes will include more pain-specific education and key elements of CBT, enhance mindful interoceptive awareness and an expanded yoga component, for which we will provide videos for home practice.

In addition, we will identify potentially eligible participants through review of our Medical Center's electronic medical records and send *letters inviting study participation using* the UCSF CTSI. Randomization for the final cohort will be performed using a computer-based assignment program, in which study staff must enter the participant ID number before randomization is revealed; assignment is then locked into the database. It will be stratified by sex, as responsiveness to mind-body interventions varies by sex. The UCSF study site of the ongoing NIH HEAL BACPAC initiative, for which both Drs [name] and [name] are key personnel, will create a large cohort of patients with cLBP (recruitment started June 2021), which can be approached for advertising our study.

MBPR will be delivered by an experienced mind-body practitioner with expert skills in mindfulness, MBSR and body awareness-enhancing approaches. Phase 1 includes a 2-day training retreat for the instructor led by [name] to prepare the MBSR instructor for the MBPR program. Home practice will be supported by audio recordings uploaded to the Insight Timer® smart phone platform. The Insight Timer application will also be used to track and record the frequency in which participants are doing a meditation practice in combination with a physical or electronic log. The instructor will use a workbook, audio recordings of guided meditation (these are standard recordings used e.g. in MBSR classes at the Los Angeles Insight Meditation Center), *Outsmart your Pain* by [name], PhD, a guide book for mindfulness with pain, and videos of yoga sequences (as outlined in handout, attached). Study participants will receive additional printed and audio support material.

**Schedule of Measures:** Participants will be assessed using computer-assisted questionnaires in the first and last week of the MBPR courses and will be followed up at 6 months for clinical outcomes. In addition we will use a mobile platform-based EMA, as detailed below.

**Meditation home practice adherence measure:** *Rationale:* All participants will be instructed to do daily home practice. Benefits of any mind-body intervention may depend on applying the class teaching to practice at home. Home practice for chronic conditions may need a higher dose than e.g. for experimental pain. We will request a minimum of 30 minutes for an expected effective duration of 20 minutes (>70%) on at least 5 days per week. *Methods:* Our research team has successfully used the free downloadable mobile app InsightTimer® to monitor adherence to home practices by asking participants to use it during home practice session. It has a variety of bell sounds that can be set for desired meditation time periods. The application includes two other features we have successfully tested at UCSF: 1) It connects with the research team in our study providing data about when and for how long a participant practiced meditation. 2) The app allows guided meditation recordings that we are preparing for home practice to be uploaded and made available to participants. Participants will log in with unique pseudonyms and a participant-specific e-mail address that is created for this study only to eliminate any risk to loss of privacy, which will be discussed during the consent process. Any identification of the

participating InsightTimer user will not be possible as the app will not use the personal e-mail of the participant and only use pseudonyms.

At the VA:

This study includes a Pain Attention Task to be preformed in the fMRI that separates insula activation during experimental heat application between different pain attention conditions.

The participants will be patients with cLBP according to the definition of the NIH Task Force on Research Standards for cLBP: pain at least half the days in the past 6 months, by using 2 questions and a human figure drawing illustrating the region between the lower posterior margin of the rib cage and the horizontal gluteal fold. Participants will have an average pain intensity in the past week of at least 4 out of 10 on the numeric rating scale (NRS). They will be recruited through advertisement in newspapers, social media and fliers, and from the current UCSF Spine Center cLBP cohort (see below).

**MRI Pain Attention Task:** The paradigm has 4 stimulus conditions presented in pseudo-random order. Individually determined, moderately painful (~47.5°C) stimuli will be delivered with a 9cm^2 thermode (Medoc) securely placed at the forearm. Subjects are instructed and trained before scanning as follows: (A: thinking) for the 'think'- condition: "think about pain stimulus and your chronic pain, its history and impact on your life, your expectation for your future life"; (B: sensing) for the 'feel'-condition: "feel the pain stimulus, be aware about how it makes you feel, its location, intensity and quality. "; (C: metacognition) for the 'reflect'-condition: "please notice whether you can observe how thoughts and emotions regarding your pain arise that may be familiar, whether they are really appropriate or not"; and (D: default) for the 'none'-condition: "do nothing specific, just wait for the stimulus to be over". The instructing cues: think, feel, reflect, and none, will be presented for 1s, followed by 20s of painful heat stimulation, followed by 39s baseline with neutral temperature to minimize habituation/ sensitization, until the start of the next trial. 7 trials of each condition will be performed for each subject. The task will be administered in four 7-min sequences.

This task has been used in prior studies without any risks for the participant.

A total of 50 participants will be enrolled into this study. 40 participants with cLBP will be enrolled into 4 consecutive MBPR classes ( $n = 10$  for each course) to iteratively refine the manualized MBPR protocol through mixed-methods evaluations after each round of MBPR. 10 participants with cLBP will be in the MBSR as the control group.

The first 30 participants enrolled in the study will be assigned to MBPR classes and the final 20 participants will be randomly assigned with ( $n = 10$ ) participants assigned to MBSR and ( $n = 10$ ) participants assigned to MBPR to test recruitment and randomization approaches.

**7.10 STANDARD CLINICAL PRACTICE: To what extent, if any, do the planned research procedures differ from the care that people would otherwise receive at this institution or the study site if not being done locally:**

MBPR is based on MBSR, a program that is part of the national guidelines for treating chronic low back pain. MBSR programs are currently delivered regularly at the Osher Center at UCSF. The differences are described above and do not affect the burden or safety of participating patients with cLBP. Phase 1 of the study developed the manual and support materials and nears completion with this application. This application is for Phase 2, the implementation of MBPR with patients.

**7.11 INSTRUMENTS: List all questionnaires, surveys, interview, or focus group guides that will be used for this study:**

If the instruments are not complete or not available because they will be developed as part of this study, describe the basic content or include an outline and submit the final versions to the IRB with a modification for approval prior to use.

Questionnaires are identical to required instruments in the larger BACPAC study of the NIH HEAL Initiative.

- 1) BACPAC Baseline Demographics *Includes HEAL required questions (22)\* only at baseline. This includes questionnaire items necessary to adjust for MRI, e.g. to fit MRI-compatible correcting eye glasses.*
- 2) PEG scale assessing pain intensity and interference (Pain, Enjoyment, General Activity) (3)\*
- 3) Generalized Anxiety Disorder (GAD-2) [Kroenke et al, 2007] (2)\*
- 4) Patient Health Questionnaire-2 (PHQ-2) [Kroenke et al, 2003 (2)\*
- 5) Tobacco, Alcohol, Prescription medication, and other Substance use (TAPS) tool (4)\*
- 6) PROMIS Physical Functioning Short Form 6b (2 items not in PROMIS-29)\*
- 7) PROMIS Sleep Disturbance 6a [Yu et al, 2011] (2 items not in PROMIS-29)\*
- 8) Sleep Duration Question [Kurina et al, 2013] (1)\*
- 9) Pain Catastrophizing Scale - short form 6 (PCS) [McWilliams, 2015] (6)\*
- 10) Patient Global Impression of Change (PGIC) (1) only at 8 weeks.
- 11) PROMIS-29+2 Profile v2.1 (PROPr) 02Jan2020 [PROMIS] (31)\*
- 12) Charlson Comorbidity Index (CCI), [MDCalc (<https://www.mdcalc.com/charlson-comorbidity-index-cci>)]\* baseline only
- 13) PainDETECT Questionnaire (PD-Q) [Freynhagen et al., 2006] (7)\*
- 14) Fear-Avoidance Beliefs Questionnaire Physical Activity (FABQ-PA) [Waddell et al., 1993] (5)\*
- 15) Chronic Pain Acceptance Questionnaire-SF8 [Fish et al. 2010] (8)\*
- 16) Multidimensional Assessment of Interoceptive Awareness (MAIA) [[name] et al., 2018] (37)
- 17) Perceived Stress Scale [Cohen et al., 1989] (4)\*
- 18) International Positive (and Negative) Affect Schedule 10-item SF [Watson et al., 1988] (5)\*
- 19) PROMIS Emotional Support 4a V2 [Tucker et al, 2014] (4)\* only baseline
- 20) Pain Self-Efficacy Questionnaire 4-item version (items 4, 6, 8, 9) [Chiarotto et al, 2016] (4)\*
- 21) Primary Care PTSD Symptom Screener [Prins et al, 2016] (1)\* only baseline
- 22) Financial Strain [Puterman et al, 2012] (1)\* only baseline
- 23) Perceived Discrimination [NIMDH] (1)\* only baseline
- 24) Expectation of Pain Relief [Cormier et al, 2016] (1)\* only baseline
- 25) Pain Anxiety Symptoms Scale - Short Form (PASS-20) - (items 6-10, 16-20) [McCracken et al. 2002] (10)\*
- 26) Five Facets Mindfulness Questionnaire (FFMQ) [Baer et al. 2006] (39)
- 27) CHILD TRAUMA QUESTIONNAIRE (CTQ) – SHORT FORM [Bernstein et al. 1995]
- 28) Ecological Moment Assessment (EMA)
- 29) Semi-structured exit interviews
- 30) Qualitative questions at 6 months, 3 items

**Attach any unpublished instruments in the 'Other Study Documents' section of the Initial Review Submission Packet form after completing the study application. Published instruments should NOT be attached.**

**7.12 \* BIOSPECIMEN COLLECTION: Are you drawing any blood or collecting other biosamples (e.g. tissue, buccal swabs, urine, saliva, hair, etc.) for analysis under this protocol and/or storage for future research: (REQUIRED)**

Yes  No

## 8.0 Drugs and Devices

### 8.1 \* DRUGS AND/OR BIOLOGICS: Are you STUDYING any drugs and/or biologics that are either approved or unapproved: (REQUIRED)

Yes  No

If you have questions about FDA requirements for drug or device research, you can send an [email](#) to request a consult.

**Note: This question is frequently answered incorrectly. If any drugs or biologics, approved or unapproved, are being administered under this protocol, you should check 'Yes' unless you are absolutely sure that NONE of the drugs are part of the research protocol. Tip: Ask the PI or the sponsor if you are not sure how to answer this question.**

### 8.3 \* MEDICAL DEVICES: Are you STUDYING any medical devices, in vitro diagnostics, or assays that are either approved or unapproved:(REQUIRED)

Yes  No

If you have questions about FDA requirements for drug or device research, you can send an [email](#) to request a consult.

## 9.0 Sample Size and Eligibility Criteria

### 9.1 ENROLLMENT TARGET: How many people will you enroll:

If there are multiple participant groups, indicate how many people will be in each group:

A total of 50 participants will be enrolled into this study. 40 participants with cLBP will be enrolled into 4 consecutive MBPR classes ( $n = 10$  for each course). 10 participants with cLBP will be in the MBSR as the control group.

Specifically, the first 30 participants of the total 50 enrolled in the study will be assigned to MBPR classes and the final 20 participants will be randomly assigned to MBSR ( $n = 10$ ) or to MBPR ( $n = 10$ ) to test recruitment and randomization approaches.

**9.3 SAMPLE SIZE JUSTIFICATION: Explain how and why the number of people was chosen. For multi-site studies, this is referring to the number that will be enrolled across all sites:**

The primary goal of this study is to prepare for a rigorous RCT comparing efficacy of the MBPR intervention to alternatives. We are not aiming to test efficacy in the current study and do not have adequate sample size for this assessment. The proposed sample sizes were selected based on the numbers we estimate will be needed to adequately refine the intervention and assess its acceptability and feasibility, and to obtain variance estimates to inform future work. However, we will conduct **exploratory analyses** to obtain estimates of ICCs of the repeated measures from linear mixed models, and run linear mixed models with pain as outcome, and an interaction between study period and psychological variables (e.g. PCS-SF, FABQ-PA, and MAIA-2) as predictors, with nested random effects of person nested within class group. Although using all participants across all iterations of MBPR is limited by variations in the intervention, with a total MBPR sample size of 40 (out of 50 total enrolled, with a control/MBSR group of  $n = 10$ ), we will have 80% power (two-tailed alpha = 0.05) to detect a statistically significant correlation if the expected coefficient of determination is 0.43 or greater.

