### 6.2 Justification of Sample Size

The primary goal of this study is to prepare for a rigorous RCT comparing efficacy of the MBPR intervention to alternatives. We are not aiming to test efficacy in the current study and do not have adequate sample size for this assessment. The proposed sample sizes were selected based on the numbers we estimate will be needed to adequately refine the intervention and assess its acceptability and feasibility, and to obtain variance estimates to inform future work. However, we will conduct **exploratory analyses** to obtain estimates of ICCs of the repeated measures from linear mixed models, and preliminary estimates looking at Pearson correlations between changes in pain outcomes and changes in psychometric scale measures that we understand to be potential mediators of change in pain intensity following mindfulness interventions, e.g. PCS-SF, FABQ-PA, and MAIA-2. Although using all participants across all iterations of MBPR is limited by variations in

the intervention, with an exploratory total MBPR sample size of 40, we will have 80% power (two-tailed alpha = 0.05) to detect a statistically significant correlation if the expected Pearson correlation coefficient comparing change scores for pain outcomes with change scores for psychometric scale measures is 0.43 or greater. If we experience a loss to follow-up rate of 10% in our classes, the sample size per subsequent class will be increased to 11 subjects.

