Hypothesis 4: Assessment of pain intensity/interference with a smartphone delivered EMA is feasible and correlates with standard pain outcome measures. Feasibility/acceptability measures are noted in the table above. We will assess the correlation of our EMA measures with the Numeric Pain Rating Scale for pain intensity, and pain interference rating. We predict a correlation of >.7. We will also perform qualitative assessment to get participants assessment of where the two approaches are similar, and where they may get differing responses.

Hypothesis 5: Assessment of meditation practice adherence is feasible using a smartphone app. At the 8-week assessment period, we will include questions about meditation practice over the prior week and compare this with the results from use of the Meditation Insight Timer data. We will ask further questions about any sessions that were not recorded using the app, and reasons for not recording. This information will be analyzed after each group, and refinements made if needed in participant instructions and other steps to encourage use of the app as consistently as possible.

Hypothesis 6: We will conduct **exploratory analyses** to test for correlations between changes in pain outcomes and scores on the PCS, TSK, CPAQ, MAIA, and FFMQ using regression models.

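### The 80% power quoted in Protocol 9.3 belongs to a change-score correlation, not to the period-by-scale interaction that 9.3 names; power for that interaction is not established

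*Protocol*

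**What the plan says.** Protocol 9.3 (sample size justification) says the team will "run linear mixed models with pain as outcome, and an interaction between study period and psychological variables", giving PCS-SF, FABQ-PA and MAIA-2 as examples, "with nested random effects of person nested within class group". It continues that, "with a total MBPR sample size of 40", "we will have 80% power (two-tailed alpha = 0.05) to detect a statistically significant correlation". The condition attached to that figure reads "if the expected coefficient of determination is 0.43 or greater". Section 9.3 does not say whether the psychological variable is the baseline score, the score at each visit or the change, nor how many periods enter.

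DSMP 6.2 (within Protocol 13.1) uses the same N, power and alpha, and the same 0.43, but for another analysis: "preliminary estimates looking at Pearson correlations between changes in pain outcomes and changes in psychometric scale measures", described there as possible mediators. The power holds "if the expected Pearson correlation coefficient comparing change scores for pain outcomes with change scores for psychometric scale measures is 0.43 or greater".

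SAP Hypothesis 6 gives a third description: "correlations between changes in pain outcomes and scores on the PCS, TSK, CPAQ, MAIA, and FFMQ using regression models". It is unclear whether the word for change governs only the pain outcomes or the scale scores too.

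Both 9.3 and DSMP 6.2 call these analyses exploratory, and justify the sample size by refinement, acceptability, feasibility and variance estimation.

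**The concern.** A power figure is a property of one test of one term. Section 9.3 puts a figure derived for a change-on-change correlation directly after a mixed model whose named term is an interaction. The interaction's null hypothesis depends on how the scale enters. Under two of the three natural choices, that null is not the absence of a link between change in the scale and change in pain.

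The study exists to prepare an RCT, and DSMP 6.2 treats these scales as candidate mechanisms. An analyst who fits 9.3 with visit or baseline scores and finds a null interaction could cite 80% power and read the result as evidence against a mechanism. In some plausible settings that test has almost no ability to detect the link.

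**Working it through.** **Inputs from the documents.** Two-sided alpha 0.05, n = 40, effect 0.43 (9.3 and DSMP 6.2). **Assumed, because no document gives them:** two visits, the variances, the test-retest correlations and the cross-sectional pain-scale correlations.

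**Step 1: reproduce the 80%.** Fisher z: power = Φ(atanh(r)·√(n − 3) − 1.960).

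- As a Pearson r of 0.43: atanh(0.43) = 0.460; √37 = 6.083; product 2.797; 2.797 − 1.960 = 0.837; Φ = 79.9%. The bias-corrected form gives 80.8% and simulation of the Pearson test 81.0%. The plan's figure reproduces.
- As a coefficient of determination of 0.43: r = √0.43 = 0.656; atanh = 0.785; 0.785 × 6.083 = 4.776; minus 1.960 = 2.816; Φ = 99.8%. This does not reproduce.
- Inverting: 80% power at n = 40 needs r of about 0.431, an R² of about 0.185.

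So the figure is the DSMP 6.2 calculation, and the label in 9.3 is a separate slip.

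**Step 2: what the interaction tests.** Code period 0/1 and write pain = b0 + b1·period + b2·x + b3·period·x + person effect. Taking the within-person difference:

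- x is the score at each visit: pain change = b1 + b2·(x1 − x0) + b3·x1. The change-on-change link sits in b2. The named term b3 is the difference in slope between visits, and is zero for a scale that tracks pain equally well at both, however strong the link.
- x is the baseline score: pain change = b1 + b3·x0. This is prediction or moderation by baseline.
- x is the person's change score: pain change = b1 + b3·(x1 − x0). Only here is b3 the change-on-change term.

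**Step 3: power of b3 with the change-change correlation fixed at 0.43, n = 40.** Random-intercept REML, 1,500 replicates per scenario, except that the test-retest 0 and 0.9 figures come from simulating the equivalent correlation test.

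| Scale enters as | Assumed structure | Power of b3 |
|---|---|---|
| Score at each visit | Stable slope; test-retest 0.3, 0.5, 0.7 | 4–6% |
| Score at each visit | Cross-sectional correlation 0.3 before, 0.5 after, post SD 1.3 | 13% |
| Score at each visit | 0.2 before, 0.5 after | 30% |
| Score at each visit | 0.1 before, 0.6 after | 70% |
| Baseline score | Stable-slope structures; test-retest 0, 0.3, 0.5, 0.7, 0.9 | 49%, 36%, 27%, 18%, 9% |
| Baseline score | The three unequal-slope structures above | 5–7% |
| Change score | All structures simulated | 80–82% |

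The first baseline row can be checked by hand. With test-retest correlation ρ and, for example, pain change driven only by scale change, the baseline score correlates with pain change at 0.43·√((1 − ρ)/2) in absolute value. At ρ = 0.5 this is 0.215; atanh = 0.218; 0.218 × 6.083 ≈ 1.33; minus 1.960 = −0.63; Φ ≈ 26%, against 27% simulated.

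A smaller run with person nested in class (300 replicates, test-retest 0.5) gave 7% for visit scores, 26% for baseline and 81% for change scores, so the class effect does not alter the picture.

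**Step 4: an alternative term.** In the same mixed model, the within-person deviation of the scale, with the person mean as a second covariate, had 80–82% power at a change correlation of 0.43. It rejected in about 5% of replicates when that correlation was 0 (4,000 replicates per scenario).

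**The case against.** The best defence has four parts.

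- **Section 9.3 does not exclude change-score entry**, and with it the interaction is the change-on-change test with about 80% power. This stands as a reason not to say the model must test the wrong hypothesis. It does not supply the missing specification: DSMP 6.2 says changes in the scales when it means changes, and 9.3 does not.
- **The change-score correlation is already planned in DSMP 6.2, with the right power.** This stands and limits the damage. It leaves one application with two analyses sharing one power figure, and an SAP with a third wording.
- **A period-by-predictor model is a legitimate exploratory question.** True, but the 80% was not computed for it.
- **The analysis is exploratory.** The SAP says significance is not expected and favours effect sizes with confidence intervals. This stands and keeps the severity moderate.

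Three stronger readings are tempting. A reader might infer that power drops to one narrow low band, such as 5–27%. The documents give no covariances that fix such a band; its ends match particular assumed cases. A reader might infer that useful scales would be dropped from the future RCT, but no passage ties their retention to this p-value. A reader might also infer an inflated false-positive rate, since with a change correlation of 0 and a baseline correlation of 0.6 the visit-score interaction can reject in about 10.5% of replicates. If that setting has unit baseline variance and an independent change of SD 0.8, the true slope goes from 0.60 to 0.6/(1 + 0.64) = 0.37. The interaction's own null is then false, and the rejections are power against a real slope difference.

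**Conclusion.** The point holds in a limited form. The 80% in 9.3 reproduces for the Pearson correlation of change scores in DSMP 6.2. It was not derived for the interaction named in 9.3, whose meaning depends on an unstated choice. Fitted with visit or baseline scores, the interaction does not test the association for which the power is quoted, and no baseline or visit-score scenario examined reached 80%. Even the 70% case is power against a slope difference.

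The mismatch in tested term follows from algebra and needs no assumed values. The power percentages rest on two visits and assumed variances and correlations, so they illustrate that power is not established rather than estimate it. The consequence is modest because the analysis is exploratory and the sample size does not depend on it. It is still worth correcting, because a stated power figure is attached to the wrong term.

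**What to change.** In Protocol 9.3 and SAP Hypothesis 6:

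1. For the change-on-change question, make the tested term the within-person effect of the scale: pain on period, the visit score minus the person's own mean, and the person mean, with the random effects already planned. Regressing pain change on scale change, in line with DSMP 6.2, serves equally well.
2. State that the 80% (n = 40, two-sided 0.05) refers to that term, with 0.43 given as a Pearson r (R² about 0.185), and remove the coefficient-of-determination label.
3. If a period-by-baseline-score interaction is wanted, list it as a separate exploratory moderator analysis with no power claim.
4. In SAP Hypothesis 6, say explicitly that change in pain is related to change in each scale, and align the wording across 9.3, DSMP 6.2 and the SAP.

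The cost is a few sentences of text. Data, software and enrolment are unchanged.
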